### Investigational Protocol: Iowa Cochlear Implant Clinical Research Center Hybrid Cochlear Implants in Severe to Profound Adults, Children, and Adolescents

#### 1 INVESTIGATIONAL PROTOCOL

The purpose of this study is to determine if individuals with residual low-frequency hearing in the severe range can develop improved speech perception by combining their residual acoustic hearing with electrical processing through a cochlear implant designed to stimulate the high-frequency basal and middle turn of the cochlea while preserving useful low-frequency acoustic hearing. To accomplish this, we propose to implant individuals with severe hearing with a Cochlear® Nucleus™ Hybrid L24 Implant or a Cochlear® Nucleus™ Hybrid S12 in the poorer ear. We believe these devices will do less damage to the Organ of Corti structures, than longer, more invasive standard cochlear implant electrodes. Two different populations will be studied under this IDE.

Population 1: 15 Adults who have a severe sensorineural hearing loss with a pure-tone average (PTA) between 60-90 dB HL between 125-1500 Hz and profound loss at higher frequencies will be implanted with the Cochlear® Nucleus™ Hybrid L24 Implant. The potential subject will present with Consonant-Nucleus-Consonant (CNC) monosyllabic word scores between 0-35% in the ear to be implanted and up to 60% understanding in the contralateral ear in the best-aided condition.

Population 2: 30 Children (ages 5-12 years) and adolescents (ages 13-15 years) who have a sensorineural hearing loss with a pure-tone average (PTA) between 70-90 dB HL between 125-1500 Hz and profound loss at higher frequencies will be implanted with the Cochlear® Nucleus™ Hybrid L24 Implant or the Cochlear® Nucleus™ Hybrid S12 Implant. Those that have hearing thresholds between 70-90 dB HL at 1500 Hz would be implanted with the less invasive shorter 10 mm Hybrid S12 in attempt to better preserve the middle frequency range. Those with hearing thresholds >90 dB HL at 1500 Hz would receive the longer 16 mm Hybrid L24 electrode. The potential subject will present with Phonetically Balanced Kindergarten (PB-K) monosyllabic word scores between 0-50% in the ear to be implanted and up to 60% understanding in the contralateral ear in the best-aided condition.

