#### 1.1 *Criteria for Inclusion in Population 1*

Criterion for selection will be subject interest in preservation of residual hearing; severe sensorineural hearing loss; lack of benefit from appropriately fit binaural hearing aids worn on a full-time basis; and realistic expectations. Qualified participants must also meet the following criteria for inclusion:

1. Eighteen year of age or older at the time of implantation.
2. Severe sensorineural hearing loss with a pure-tone average (PTA) between 60-90 dB HL between 125-1500 Hz and profound loss at higher frequencies in the ear to be implanted.

3. Speech Perception:
  - a. The Consonant-Nucleus-Consonant (CNC) word recognition score between 0% and 35% inclusive (i.e.,  $0\% \leq \text{score} \leq 35\%$ ) in the ear to be implanted.
  - b. The CNC word recognition score in the contralateral ear equal to or better than, in the ear to be implanted but not more than 60% in the best-aided condition.
4. English spoken as a primary language.
5. Willingness to comply with all study requirements.
6. Minimum of 30 day hearing aid trial with appropriately fit hearing aids worn on a full-time basis (8 hours per day).
7. Patent cochlea and normal cochlear anatomy.

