### ***1.2 Criteria for Inclusion in Population 2***

Criterion for selection will be parent interest in preservation of residual hearing; severe post-lingual onset of sensorineural hearing loss; lack of benefit from appropriately fit binaural hearing aids worn on a full-time basis; and supportive family dynamics. Qualified participants must also meet the following criteria for inclusion:

1. Five to fifteen years of age at the time of implantation.
2. Severe sensorineural hearing loss with a pure-tone average (PTA) between 70-90 dB HL between 125-1500 Hz and profound loss at higher frequencies in the ear to be implanted.
3. Speech Perception:
  - a. The Phonetically Balanced-Kindergarten (PB-K) word recognition score between 0% and 50% inclusive (i.e.,  $0\% \leq \text{score} \leq 50\%$ ) in the ear to be implanted.
  - b. The PB-K word recognition score in the contralateral ear equal to or better than, in the ear to be implanted but not more than 60%.
4. English spoken as a primary language.
5. Willingness to comply with all study requirements.
6. Minimum of 30-day hearing aid trial with appropriately fit hearing aids worn on a full-time basis (8 hours per day)..
7. Patent cochlea and normal cochlear anatomy.
8. Must be in a habilitation/educational program with an emphasis on spoken language development.

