Fifteen children (ages 5-12 years) and adolescents (ages 13-15 years) who have a sensorineural hearing loss with a PTA between 70-90 dB HL between 125-1500 Hz, a hearing *threshold* >90 dB HL at 1500 Hz, and profound loss at higher frequencies will be implanted with the *Cochlear® Nucleus™ Hybrid L24 Implant*. In addition, in attempt to better preserve the middle frequency range, fifteen children (ages 5-12 years) and adolescents (ages 13-15 years) who have a sensorineural hearing loss with a pure-tone average PTA between 70-90 dB HL between 125-1500 Hz, a hearing *threshold* ≤90 dB HL at 1500 Hz, and profound loss at higher frequencies will be implanted with the *Cochlear® Nucleus™ Hybrid S12 Implant*. All potential subjects will present with Phonetically Balanced Kindergarten (PB-K) monosyllabic word scores between 0-50% in the ear to be implanted and up to 60% understanding in the contralateral ear in the best-aided condition.

Postoperatively, electric alone, hybrid, and combined listening (i.e., electric and acoustic together) modes will be compared to evaluate the usefulness of adding the electric stimulation while preserving residual hearing for acoustic stimulation. The following defines the various modes referenced throughout the course of this text:

Acoustic Stimulation: Use of the word "acoustic" refers to sound only delivered with amplification.

Electric Stimulation: Use of the word "electric" refers to sound delivered via a cochlear implant only.

Hybrid Stimulation: Use of acoustic hearing, with amplification, in addition to electric hearing via a cochlear implant in the same ear.

Combined Stimulation: Use of acoustic hearing bilaterally, with amplification, in addition to electric hearing via a cochlear implant.

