frequencies. According to Turner (2006), provision of amplification for lower frequencies does not appear to be constrained to the same extent by thresholds for lower frequencies (< 2500 Hz), though no proposal is made as to when such a constraint might occur.

Taking a conservative approach, useful hearing will be defined by hearing thresholds better than 90 dB HL for this study. Hearing levels 90 dB HL or poorer are considered to not be aidable, from an amplification perspective.

It is recognized that prescriptive methods are based on average requirements, and that individuals may find deviations from target values optimal for sound loudness, quality, or clarity. For example, individual adjustments required to relieve occlusion effects will be permitted.

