### 2.3.5 Audiological Assessment

The degree of hearing loss will be determined by standard audiometric technique. Audiological assessment will include unaided and aided audiometric thresholds.

Unaided audiometric thresholds will be obtained for each ear, with insert earphones, when possible, using the standard audiometric technique for pure-tone air-conduction testing. Aided audiometric thresholds will be obtained for each ear in the sound-field using frequency-modulated (FM) noise and using the standard audiometric technique with the speakers positioned at 0° azimuth relative to the subject's head. As these subjects may have some low-frequency hearing bilaterally it is important that appropriate consideration be made for masking/plugging the contralateral ear during aided testing when a unilateral ear is being tested. Testing, for both ears, will include the following:

- Unaided Air Conduction thresholds at 125, 250, 500, 750, 1000, 1500, 2000, 3000, 4000, 6000, and 8000 Hz;
- Bone conduction thresholds at 125, 250, 500, 750, 1000, 1500, 2000, and 4000 Hz;
- Aided Air Conduction thresholds at 125, 250, 500, 750, 1000, 1500, 2000, 3000, and 4000 Hz;
- Tympanometry in each ear.

The CNC word recognition test in quiet (at 60 dB A) will be administered in aided conditions (right hearing aid alone and left hearing aid alone) to adults to determine if a candidate meets the speech perception criteria. Candidates must demonstrate a lack of word understanding, defined as preoperative aided CNC word recognition test recognition scores between 0% and 35% inclusive in the ear to be implanted and ≤ 60% in the contralateral ear. The non-test ear will be plugged for all test conditions.

The PB-K word recognition test in quiet (at 60 dB A) will be administered in aided conditions (right hearing aid alone and left hearing aid alone) to adults determine if a candidate meets the speech perception criteria. Candidates must demonstrate a lack of word understanding, defined as preoperative aided PB-K word recognition test recognition scores between 0% and 50% inclusive in the ear to be implanted and ≤ 60% in the contralateral ear. The non-test ear will be plugged for all test conditions.

---

 For unilateral test conditions, the ear contralateral to the test ear will need to be occluded with sound-attenuated ear plugs for aided speech perception testing.

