## **2.4 Postoperative Procedures**

### **2.4.1 Device Activation**

One day prior to activation, subjects without a contraindication to glucocorticoid therapy will be started on prednisone 1mg/kg for 1 week. Subjects will be asked to undergo weekly audiometric testing for one month to monitor acoustic hearing. If drops in threshold of 15 dB HL or more at 125, 250, or 500 are observed, additional prednisone 1mg/kg will be prescribed for 14 days with a gradual taper off over the following week.

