#### 2.5 Adverse Effects

Adverse effects are any undesirable clinical or medical occurrence associated with use of the device or participation in the study. Any adverse effects are to be reported to the FDA and our IRB via the "Adverse Effects Form". The Primary Investigator will be required to verify that there are or there are no adverse effects to report.

Adverse effects will be reported if observed, even if acknowledged as risk factors in the consent. Adverse effects include:

1. Sudden changes in residual low-frequency hearing. Specifically, a PTA at 125, 250, 500 HZ that is  $\geq 30$  dB HL.
2. Total loss of residual hearing
3. Vertigo, dizziness, or balance problems that did not exist preoperatively or worsened postoperatively
4. Facial nerve problems
5. Meningitis
6. Perilymphatic fistulae
7. Tinnitus that did not exist preoperatively or worsened postoperatively
8. Implant Migration/Extrusion
9. Skin flap problems
10. Device-related/programming problems
11. Infection requiring explantation
12. Device failure requiring explantation

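### Adverse-effect item 1 is headed as a sudden change in low-frequency hearing but defined as an absolute level of at least 30 dB HL, which nearly every eligible ear meets before surgery

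*Protocol*

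**What the plan says.** Section 2.5 lists the adverse effects to be reported to the FDA and the IRB. Item 1 reads "Sudden changes in residual low-frequency hearing. Specifically, a PTA at 125, 250, 500 HZ that is" ≥30 dB HL. It names no reference audiogram and no time window. Item 2, total loss of residual hearing, has no dB definition. Items 3 (vertigo, dizziness, balance) and 7 (tinnitus) do refer to the preoperative state.

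The entry criteria for the ear to be implanted are:
- Adults (section 1.1): "Severe sensorineural hearing loss with a pure-tone average (PTA) between 60-90 dB HL between 125-1500 Hz".
- Children and adolescents (section 1.2): "Severe sensorineural hearing loss with a pure-tone average (PTA) between 70-90 dB HL between 125-1500 Hz".

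Section 1 describes the target population as "individuals with residual low-frequency hearing in the severe range".

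Other sections do express hearing loss as a change. Section 2.4.1 has "If drops in threshold of 15 dB HL or more at 125, 250, or 500 are observed". Section 2.4.3 uses a downward shift of more than 10 dB and, under Hearing Aid Verification, a shift of more than 10 dB at two or more frequencies, limited to that purpose. These trigger treatment or refitting of amplification, not adverse-effect reporting.

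**The concern.** The heading and the definition of item 1 describe different things. A change needs two audiograms, whereas a PTA of at least 30 dB HL can be read off one. The level chosen also lies far below the PTA required for entry, so the numeric criterion mostly restates the entry condition.

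Keeping low-frequency acoustic hearing is the purpose of these electrodes, and item 1 is the only place where a reportable hearing loss has a number. Followed as written, that number is met by a preserved ear and by an ear that lost 30 dB. A reader who infers a shift must choose the reference audiogram. Suppose an ear loses 10 dB at each of three successive visits. Against the preoperative audiogram it has lost 30 dB and is reported. Against the previous visit it never loses more than 10 dB and is not. Two careful readers could therefore report different events from the same audiograms.

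**Working it through.** The protocol gives no event rate or power figure here, so there is nothing of its own to reproduce. The check is whether an eligible ear can be below 30 dB HL at 125-500 Hz before surgery.

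**Inputs**
- Item 1 level: 30 dB HL, mean of 125, 250 and 500 Hz (section 2.5).
- Lowest eligible 125-1500 Hz PTA: 60 dB HL in adults (section 1.1), 70 dB HL in children and adolescents (section 1.2).
- Tested frequencies: "Unaided Air Conduction thresholds at 125, 250, 500, 750, 1000, 1500, 2000, 3000, 4000, 6000, and 8000 Hz" (section 2.3.5). Six of these lie in the 125-1500 Hz band.
- S12 children have a 1500 Hz threshold "≤90 dB HL at 1500 Hz, and profound loss at higher frequencies will be implanted with the" S12 (section 2.1).
- *Assumption:* the entry PTA is the plain mean of the six frequencies in the band. The protocol does not list them, so a five-frequency version without 750 Hz is also shown.

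**Boundary arithmetic.** Let L be the mean of 125, 250 and 500 Hz, and U the mean of the other frequencies in the PTA.

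| PTA definition | Condition | Adults (PTA ≥ 60) | Children (PTA ≥ 70) |
|---|---|---|---|
| Six frequencies | (3L + 3U)/6 ≥ PTA with L < 30 | U > (360 − 90)/3 = 90 | U > (420 − 90)/3 = 110 |
| Five, without 750 Hz | (3L + 2U)/5 ≥ PTA with L < 30 | U > (300 − 90)/2 = 105 | U > (350 − 90)/2 = 130 |

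These are the easiest cases, at the lowest eligible PTA. At a six-frequency PTA of 75, U would have to exceed (450 − 90)/3 = 120 dB HL.

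**S12 children.** With 1500 Hz at 90 dB HL or better, the 750 and 1000 Hz thresholds would have to average more than (420 − 90 − 90)/2 = 120 dB HL, worse than at 1500 Hz. If thresholds do not improve with rising frequency, U is at most 90, so L is at least (420 − 270)/3 = 50 dB HL and every such ear meets item 1.

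**An ear that escapes.** An adult with 25, 25, 30, 80, 100 and 110 dB HL has a PTA of 370/6 = 61.7 and is within the PTA range. L = 80/3 = 26.7 and U = 290/3 = 96.7. That U lies beyond the limit in section 2.3.4, where "useful hearing will be defined by hearing thresholds better than 90 dB HL for this study". Even here, a 10 dB worsening at one low frequency gives L = 90/3 = 30 and meets item 1, although the PTA has moved by only 3.3 dB.

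**How common such shapes are.** The protocol gives no baseline audiogram distribution. As an illustration, I took every flat or sloping six-point audiogram in 5 dB steps, from 10 dB HL to an assumed maximum of 110 or 120 dB HL, and kept those within the entry PTA range. Shares with L ≥ 30 dB HL:

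| Group | Six freq., max 110 | Six freq., max 120 | Five freq., max 110 | Five freq., max 120 |
|---|---|---|---|---|
| Adults | 96.6% | 94.3% | 99.4% | 96.9% |
| Children | 100% | 99.6% | 100% | 100% |
| S12 children | 100% | 100% | 100% | 100% |

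Patterns are weighted equally, so these are not prevalence estimates. A second illustration took the PTA as uniform over the entry range and the gap U − L as normal. Mean gaps of 20 to 50 dB (SD 10-20) gave about 93-100% of adults and 98-100% of children already at or above 30 dB HL. An extreme mean gap of 60 dB (SD 20) gave about 87% and 96%.

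If the 60-90 or 70-90 dB HL range is meant to hold at each frequency, every eligible ear meets item 1.

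**The case against.** The strongest reply is that item 1 should be read whole. Its heading requires a sudden change, and section 2.5 defines an adverse effect as an occurrence associated with the device or the study, so an unchanged ear has nothing to report. Section 2.4.1 also attaches dB HL to a drop at the same three frequencies, which suggests that 30 dB HL under this heading means a 30 dB shift. The list is not exhaustive, undesirable occurrences are reportable in any case, and the audiograms allow any shift to be reconstructed later.

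Part of this stands. A shift is a plausible intention, the general reporting duty lessens the harm, and different cut-offs for treatment, refitting and reporting are not in themselves a contradiction. Section 2.3.4 also expects some individuals with very good low-frequency hearing, so *nearly every* is the right strength, not *every*.

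It does not rescue the wording. If the heading also limits the item, the 30 dB level adds almost nothing, because almost any sudden change then qualifies whatever its size. If a shift was meant, both the word and the reference audiogram are missing, although items 3 and 7 of the same list name the preoperative state. The Adverse Effects Form might settle the comparison, but it is not in the text available, and the protocol's own definition would still be wrong.

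**Conclusion.** The point holds: item 1 is wrong as written. Its numeric criterion is a level that nearly every eligible ear meets before implantation, so it cannot identify partial loss of residual hearing. The boundary figures (upper-frequency means above 90 dB HL in adults and 110 dB HL in children) rest only on reading the entry PTA as a six-frequency mean. Leaving out 750 Hz raises them to 105 and 130. The percentages depend on assumed audiogram shapes and serve only as illustration.

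The consequence is limited to the reporting of partial loss. Total loss is a separate item, and the protocol plans no event-rate analysis on item 1. It should still be fixed, because this is the only numeric reporting criterion for the main hazard of a hearing-preservation device.

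**What to change.** Restate item 1 as a worsening, in dB, of the unaided 125/250/500 Hz PTA in the implanted ear relative to a named reference audiogram. The preoperative one is the natural candidate, since section 2.3.5 already collects it. The sponsor should confirm whether 30 dB was meant as the size of that shift, and whether loss that builds up over several visits counts as well as a sudden drop. The wording should be reconciled with sections 2.4.1 and 2.4.3, so that it is clear which shift is reported and which serves another purpose. No position is taken here on the treatment triggers themselves.

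The cost is a short rewording. The thresholds needed are already taken before surgery, weekly in the first month after activation and at every follow-up interval (section 2.4.3).

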#### 2.4.3 Audiologic Follow-up

##### Audiological Testing:

Unaided audiometric thresholds will be obtained for each ear, with insert earphones whenever possible, using the standard audiometric technique for pure-tone air-conduction testing. During the first month after activation of the Hybrid implant, subjects will be seen on a weekly basis to measure residual acoustic hearing. If more than a 10 dB downward threshold shift is identified, oral prednisone 1mg/kg once a day for 7 days will be prescribed. If hearing is regained or continues to fluctuate, the treating physician and the patient would discuss another trial with the prednisone. If after use of the prednisone there is no change in hearing, the prednisone will be stopped. Additional audiologic follow-up will occur at intervals of 3, 6, 12, and 24 months in adults and at intervals of 4, 8, 12, 18, 24 months, and annually thereafter for three years in children and adolescents.

Unaided (and aided if necessary) testing, for both ears, will include the following:

- Unaided Air Conduction thresholds at 125, 250, 500, 750, 1000, 1500, 2000, 3000, 4000, 6000, and 8000 Hz;
- Bone conduction thresholds at 125, 250, 500, 750, 1000, 1500, 2000, and 4000 Hz;

- Aided Air Conduction thresholds at 125, 250, 500, 750, 1000, 1500, 2000, 3000, and 4000 Hz;

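### The only quantified hearing-loss adverse effect covers 125, 250 and 500 Hz, so a partial loss in the middle frequencies that the S12 is chosen to preserve has no defined reporting threshold

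*Protocol*

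**What the plan says.** Two items in the adverse-effect list of Protocol section 2.5 concern hearing. Item 1 reads "Sudden changes in residual low-frequency hearing. Specifically, a PTA at 125, 250, 500 HZ that is" at or above 30 dB HL. Item 2 is total loss of residual hearing, with no frequencies given. No listed item names a partial loss above 500 Hz.

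The same section opens with a wide definition: "Adverse effects are any undesirable clinical or medical occurrence associated with use of the device or participation in the study". It asks for every such effect to be reported to the FDA and the IRB, including risks already named in the consent, and it introduces the list with "Adverse effects include".

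Sections 1 and 2.1 give the reason for using two electrodes in children. Section 1 says that those with better hearing at 1500 Hz "would be implanted with the less invasive shorter 10 mm Hybrid S12 in attempt to better preserve the middle frequency range". Section 2.1 repeats the reason ("in attempt to better preserve the middle frequency range, fifteen children") and sets the dividing line at 90 dB HL at 1500 Hz. Eligibility in Population 2 (section 1.2) uses a pure-tone average (PTA) of 70-90 dB HL between 125 and 1500 Hz.

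Section 2.4.3 schedules follow-up audiometry in both ears, including "Unaided Air Conduction thresholds at 125, 250, 500, 750, 1000, 1500, 2000, 3000, 4000, 6000, and 8000 Hz".

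**The concern.** The reason for choosing the S12 and the criterion meant to record hearing harm look at different parts of the audiogram. The S12 is chosen for the middle frequencies, and the reporting criterion stops at 500 Hz. A child who loses middle-frequency hearing in the implanted ear but keeps 125-500 Hz shows no change on item 1 and does not meet item 2.

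What is at stake is consistency. Whether such a loss enters the adverse-effect record depends on how each case is judged against the general definition, so two children with the same loss could be recorded differently. Counts of hearing events by electrode would then be a poor guide to the harm that the shorter array is meant to reduce.

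**Working it through.** The protocol states no figure to reproduce. The check compares the frequencies in each rule and then does simple arithmetic on an example audiogram.

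**Inputs from the protocol**
- Item 1 frequencies: 125, 250, 500 Hz (2.5).
- S12 selection: 1500 Hz threshold of 90 dB HL or better (2.1).
- Eligible PTA in children: 70-90 dB HL between 125 and 1500 Hz (1.2).
- Follow-up frequencies: include 750, 1000 and 1500 Hz (2.4.3).

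**Assumptions**
- The eligibility PTA is the equally weighted mean of 125, 250, 500, 750, 1000 and 1500 Hz. The protocol gives only the range.
- The middle frequencies are taken as 750, 1000 and 1500 Hz. The protocol does not define them, although 1500 Hz is its own selection point.
- The audiograms are illustrative.

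**Formulas**
- Low PTA = (T125 + T250 + T500)/3
- Middle PTA = (T750 + T1000 + T1500)/3
- Six-frequency PTA = sum of all six thresholds/6

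The low PTA contains no term above 500 Hz, so its change is zero whatever happens at 750-1500 Hz, provided 125-500 Hz holds.

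**Example 1**, thresholds at 125/250/500/750/1000/1500 Hz
- Before: 70/70/75/80/80/85. After: 70/70/75/110/110/115.
- Low PTA: (70+70+75)/3 = 71.7 before and after, change 0.
- Middle PTA: 245/3 = 81.7 before, 335/3 = 111.7 after, change +30.0.
- Six-frequency PTA: 460/6 = 76.7 before, 550/6 = 91.7 after, change +15.0.

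The child is eligible (76.7 lies within 70-90) and qualifies for the S12 (85 at 1500 Hz). All three middle thresholds end above 90 dB HL, the protocol's limit for aidable hearing.

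**Example 2**
- Before: 60/65/70/80/85/90. After: 60/65/70/120/120/120.
- Low PTA: 195/3 = 65.0 before and after, change 0.
- Middle PTA: 255/3 = 85.0 before, 360/3 = 120.0 after, change +35.0.
- Six-frequency PTA: 450/6 = 75.0 before, 555/6 = 92.5 after, change +17.5.

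**Do other rules fill the gap?**
- Section 2.4.1 has a trigger ("If drops in threshold of 15 dB HL or more at 125, 250, or 500 are observed") for treatment, at the same three frequencies.
- Section 2.4.3 has a treatment trigger of more than 10 dB, with no frequency named.
- Hearing Aid Verification, in the same section, defines a shift of more than 10 dB at two or more frequencies, expressly for refitting only.

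None of the three is an adverse-effect reporting criterion.

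**The case against.** A reader might infer that a middle-frequency loss is never reportable and that the FDA and IRB would not hear of it. The text does not support that. The definition in 2.5 is broad, the list is not stated to be exhaustive, and known risks must still be reported. An investigator could report the loss under that definition. What is absent is a stated threshold, not the possibility of reporting.

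A reader might also infer that the S12 group could finish with no hearing adverse effect recorded. Read literally, item 1 is a level of 30 dB HL or more, and Example 1 meets it at 71.7 both before and after surgery. That wording is a separate problem. It does not rescue the criterion here, because a condition already met before surgery does not signal a later loss either.

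Nor would the loss be invisible. Thresholds at 750, 1000 and 1500 Hz are measured at 4, 8, 12, 18 and 24 months and then annually for three years, and residual hearing is measured weekly in the first month after activation. Preservation by electrode can be summarised from those audiograms, and a statistical analysis plan may provide for it. The limitation concerns the adverse-effect record only.

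Finally, the stated aim of the study and the device description in section 2.2 both stress low-frequency hearing, so a low-frequency item is a sensible choice. That stands as a reason to keep item 1. It does not explain why the specific reason for giving children the S12 has no matching item.

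**Conclusion.** The point holds as a gap in definition. The only quantified hearing-loss adverse effect does not respond to a partial loss above 500 Hz, and reporting of such a loss is left to judgement under the general definition. Adverse-effect counts would therefore not capture it consistently and could not support a comparison of S12 with L24 on it.

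The reach is limited. It would be wrong to say that all fifteen S12 children are affected: the gap matters only for a child who loses middle frequencies while keeping 125-500 Hz, and the protocol gives no rate for that. The example shifts depend on invented audiograms and on taking the middle frequencies as 750-1500 Hz. The zero change in the low PTA depends only on 125-500 Hz being kept. This is an inexpensive improvement worth making, and it does not invalidate the safety monitoring.

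**What to change.** In section 2.5 and on the Adverse Effects Form, add a separate item: worsening from the preoperative audiogram, in the implanted ear, of the average threshold at 750, 1000 and 1500 Hz. The sponsor should set the size of shift that counts. Tabulate it by electrode type beside the 125-500 Hz item. A shift in the average is easier to apply than loss of aidable hearing at 1500 Hz, because the protocol treats a threshold of exactly 90 dB HL differently in 2.3.4 (not aidable) and in the Acoustic Fitting text of 2.4.1 (only above 90 is not aidable).

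The cost is one line in the list and on the form, and somewhat more hearing events reported. No test or visit is added, since the thresholds are already collected.

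Separately, the threshold-shift triggers in 2.4.1 (15 dB or more at 125, 250 or 500) and 2.4.3 (more than 10 dB, no frequency named) differ, and the sponsor must reconcile them.

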#### **Acoustic Fitting:**

The acoustic component of the Hybrid sound processor will be appropriately fit using the NAL-NL1 for adults and DSL for children and adolescents (as used preoperatively for the acoustic hearing aids) to assess the degree to which real-ear targets are met for each subject. Fitting methodology with the acoustic component of the Hybrid sound processor is unchanged from that of conventional acoustic hearing aids.

The basic programming approach will be to assign frequency channels to the Hybrid electrode array that supplement the acoustic sensitivity. In other words, the frequency assignment of the electrical stimulation will begin at the frequency where acoustic hearing is no longer useful. For this purpose, hearing thresholds greater than 90 dB HL will be considered not useful from an amplification perspective and not aidable acoustically. For example, if the subject's hearing in the implanted ear is more than 90 dB HL for frequencies at and above 1000 Hz (i.e., useful acoustic hearing up to 750 Hz), the lower frequency boundary for electric stimulation will be set as close as possible to 750 Hz (i.e., the last aidable frequency). That is, electrical stimulation will be provided for inputs from around 750 to 8000 Hz and acoustic for frequencies at and below 750 Hz. Thus, there will be minimal overlap between the acoustic and the electric signals.

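### The low-frequency hearing item in section 2.5 gives a level that nearly every eligible ear meets before surgery; read instead as a 30 dB change, it can miss drops that the protocol treats with prednisone

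*Protocol*

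**What the plan says.** Section 2.5 opens broadly: "Adverse effects are any undesirable clinical or medical occurrence associated with use of the device or participation in the study". It then says "Adverse effects will be reported if observed, even if acknowledged as risk factors in the consent. Adverse effects include", followed by twelve items. Two of them concern loss of hearing:

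- Item 1: "Sudden changes in residual low-frequency hearing". The next sentence narrows it: "Specifically, a PTA at 125, 250, 500 HZ that is" at least 30 dB HL. No baseline audiogram, size of shift or ear is named.
- Item 2: "Total loss of residual hearing". Total is not defined.

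Two other sections act on smaller hearing drops:

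- Section 2.4.1: "If drops in threshold of 15 dB HL or more at 125, 250, or 500 are observed", additional prednisone is prescribed for 14 days with a taper over the following week.
- Section 2.4.3: "If more than a 10 dB downward threshold shift is identified, oral prednisone 1mg/kg once a day for 7 days will be prescribed". No frequency is named.

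On the limit of useful hearing, the acoustic fitting text in section 2.4.1 says "hearing thresholds greater than 90 dB HL will be considered not useful from an amplification perspective and not aidable acoustically". Section 2.3.4 puts the limit at 90 dB HL or poorer, so the two differ only at exactly 90.

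**The concern.** Preserving low-frequency acoustic hearing is the reason for using these electrodes, and losing it is a main foreseeable harm. Up to 45 people are to be implanted, 30 of them children or adolescents. Sections 2.7 and 2.8 measure success by speech perception, localization, music and, for children, speech and language. Hearing preservation is not among the success measures named there, so the section 2.5 report is the route this document names for bringing hearing loss to the FDA and the IRB.

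The one quantified hearing item in that report has a difficulty on either reading. As a level it does not separate a stable ear from one that has lost hearing. As a change it is set on a different measure (a three-frequency average) and at a larger size than the drops the protocol acts on with a systemic drug. Anyone completing the form must then supply a rule, and different people may supply different ones.

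**Working it through.** The plan gives no derived figure to reproduce; the check is threshold arithmetic.

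**Inputs.** Item 1: average of 125, 250 and 500 Hz at least 30 dB HL (section 2.5). Entry average over 125-1500 Hz: 60-90 dB HL in adults (1.1), 70-90 dB HL in children (1.2). Prednisone triggers: a drop of at least 15 dB at any one of 125, 250 or 500 Hz (2.4.1), or a shift of more than 10 dB (2.4.3). Limit of aidable hearing: 90 dB HL (2.3.4, 2.4.1).

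**Reading A: 30 dB HL is a level, as written.** The protocol does not say which frequencies form the entry average. I assume the six tested in that range (125, 250, 500, 750, 1000, 1500 Hz). Let P be the entry average, L the mean of the lower three and H the mean of the upper three. Then P = (L + H)/2, so L < 30 requires H > 2P − 30.

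- Adult at the floor, P = 60: H must exceed 2 × 60 − 30 = 90 dB HL.
- Child at the floor, P = 70: H must exceed 2 × 70 − 30 = 110 dB HL.
- S12 child, whose 1500 Hz threshold is at most 90 dB HL (2.1): the mean of 750 and 1000 Hz must exceed (3 × 110 − 90)/2 = 120 dB HL.

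These are the mildest eligible averages; at higher P the requirement is steeper. So an ear starts below the line only with near-normal or mildly impaired low frequencies and a very steep fall by 750 Hz. Nearly every eligible ear meets item 1 before surgery. An ear above the line stays above it whether or not it then loses hearing.

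**Reading B: 30 dB is a change in the average (an assumption).** Mean change = sum of the three drops / 3, so 30 dB needs drops summing to 90 dB.

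| Drops at 125/250/500 Hz (dB) | Mean change (dB) | Prednisone triggers met | 30 dB change met |
|---|---|---|---|
| 15/0/0 | 15/3 = 5 | both | no |
| 15/15/15 | 45/3 = 15 | both | no |
| 15/20/25 | 60/3 = 20 | both | no |
| 25/25/25 | 75/3 = 25 | both | no |
| 30/30/25 | 85/3 = 28.3 | both | no |

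What such a drop means for usable hearing depends on where the ear started:

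- 70/75/80 with drops 15/20/25 becomes 85/95/105. The average goes from 75 to 95, a change of 20 dB. 250 and 500 Hz now exceed 90 dB HL. Item 1 is not met, and item 2 is not met because 125 Hz still responds at 85.
- 65/70/75 with 25 dB throughout becomes 90/95/100, a mean change of 25 dB. All three are non-aidable by section 2.3.4, two of three by section 2.4.1.
- 50/55/60 with drops 30/30/25 becomes 80/85/85, a mean change of 28.3 dB. None passes 90 dB HL.

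**The triggers side by side.** Sections 2.4.1 and 2.4.3 both concern the first month of weekly testing but differ on the size of drop, on whether frequencies are named, and on the prednisone course. The protocol therefore has no single treatment criterion to which a reporting rule could yet be tied.

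**The case against.** A reader might infer that treated drops are not adverse effects under this protocol and go unreported. The text does not support that. The general definition covers any undesirable occurrence, reporting is required when one is observed, the list is introduced as inclusive rather than closed, and the principal investigator must verify whether there is anything to report. Nothing exempts a smaller drop.

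Nor does the document show that the report would contain few or no hearing events. Read as written, item 1 errs the other way, because it is met almost always. The audiograms exist whatever goes on the form, and an analysis plan that is not shown may use them.

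Loss of most aidable hearing is not shown either. The examples cover 125-500 Hz only, while 750-1500 Hz may still be aidable, and the result depends on baseline.

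Prednisone is also an imperfect marker of harm: section 2.4.1 starts it in every subject without a contraindication the day before activation. A treatment trigger more sensitive than an adverse-effect line can be a deliberate choice.

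These points stand and limit the claim, but they do not rescue item 1. Its opening word narrows the hearing event to one figure, and that figure is unusable as a level. The change reading remains an inference, though the subject of item 1 favours it, and section 2.4.1 also writes a drop in dB HL. On that reading, a broad definition followed by a specific 30 dB line leaves smaller drops to each person's judgement.

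**Conclusion.** The point holds in a limited form. As written, item 1 cannot identify a hearing-loss event, because nearly all of the up to 45 ears would meet it before surgery. This rests on the six-frequency reading of the entry average. If a 30 dB change was intended, drops that meet both prednisone triggers can average anywhere from 5 to 28.3 dB (in 5 dB steps) and miss item 1. Some of these take two or three of the low frequencies beyond the protocol's aidable limit without being a total loss.

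The consequence is that hearing-event counts may be incomplete and not comparable between subjects or between the L24 and S12. How many events would be affected cannot be derived from the document, which gives no rate of hearing drops.

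**What to change.** 1. In item 1, state whether 30 dB is a level or a change and, if a change, from which baseline audiogram.
2. Reconcile sections 2.4.1, 2.4.3 and 2.5 so that it is clear which drops prompt treatment and which are reportable. Which trigger or course applies is for the sponsor to settle.
3. Add a separate, reporting-only item to section 2.5: any drop in the implanted ear that meets the reconciled prednisone criterion, at any visit and whether or not it recovers, with date, frequencies, size and outcome. Tabulate these by device, apart from the 30 dB item.

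No change to treatment is proposed. The cost is a few lines in the protocol and one form per event; the thresholds are already measured weekly in the first month and at each scheduled follow-up. The drawback is that some small single-frequency drops will be measurement error, which is the reason for listing them separately.
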